ACTION Clinical Study Protocol

**A phase II triAl of Cabozantinib for hepaTocellular
carcInoma patients intolerant to sorafenib treatment or
first line treatment different to sorafeNib. (ACTION trial)**

NCT: NCT04316182

Version 4.0 – 15 July 2021

TITLE PAGE

ACTION Clinical Study Protocol

EUDRACT: 2019-004991-20

A phase II triAl of Cabozantinib for hepaTocellular carcinoma patients intolerant to sorafenib treatment or first line treatment different to sorafeNib. (ACTION trial)

| | |
|--------------------|------------------------------|
| Version and status | Version 3.0 – 8 July 2020 |
| | Version 3.1 – 27 August 2020 |
| | Version 4.0 – 15 July 2021 |

Study Sponsor: Fundació Clinic per a la Recerca Biomèdica
Principal Investigators: [name]
Affiliation: BCLC group. Liver Unit. ICMMD. CIBEREHD. IDIBAPS. Hospital Clínic
[name]
[contact]
[contact]
email: [contact]

The study will be conducted in compliance with the protocol, ICH-GCP and any applicable regulatory requirement.

The information provided in this document is strictly confidential and is intended solely for the guidance of the clinical investigation. Reproduction or disclosure of this document – whether in part or full – to parties not associated with the clinical investigation or its use for any other purpose without prior written consent of the sponsor is not permitted.

SYNOPSIS

| Study Title (Full) | |
|--|------------------------------------|
| A phase II trial of Cabozantinib for hepatocellular carcinoma patients intolerant to sorafenib treatment or other First-Line treatment different to sorafenib (ACTION trial) | |
| Related Product | |
| CABOZANTINIB | |
| Indication | |
| Patients with HCC intolerant to sorafenib according to the RESORCE trial definition or those patients who received other first-line treatment. | |
| Phase of Study | Phase IIa |
| Countries | Spain |
| Retrospective or prospective study | Prospective |
| Planned number of sites/ subjects | 7 sites / 40 patients |
| Blinding & Control | non-randomized, non-blinded |
| Study Type and Design | |
| Single arm, interventional, prospective study. | |
| Rationale | |

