⁵ Including height (only at screening visit) weight, body temperature, respiratory rate, seated blood pressure, heart rate and oxygen saturation (at rest and after mild exercise)

⁶AST, ALT, GGT, Alkaline Phosphatase alkaline phosphatase, Total Bilirubin, Direct Bilirubin, Indirect Bilirubin, Albumin, Creatinine, Alpha alpha fetoprotein, Calcium, Sodium, Potassium, Glucose, Uric Acid, triglycerides, Total Protein, Lipase, Amylase, Magnesium, Phosphate, lactic dehydrogenase LDH, Chloride, Glomerular filtration rate.

⁷Complete blood count with differential

⁸All the samples included in this section, will be centrally analyzed in a second-study

⁹Other laboratory blood tests will include peripheral Blood Mononuclear Cells (PBMCs) immunophenotyping, serum biomarker analysis, polymorphism detection associated with treatment response/resistance, circulating-free DNA analysis, circulating mRNA/miRNA. In case of any cabozantinib dose reduction a blood sample for PBMCs and serum biomarker analysis is recommended but no mandatory. Serum biomarker will be analyzed at each cabozantinib dose reduction. For details see the laboratory manual.

[figure not shown]
¹⁰Other liver tissue analysis will include tumor and non-tumor infiltrated immune cell population characterization (fresh tissue from biopsy analyzed in situ in each recruiting center) and tumor and non-tumor cell transcriptome analysis (samples can be frozen and stored until analysis). Note that these samples will be obtained accordingly to the time point of "fresh tumor biopsy" but all the analysis will be performed in a second-study.

¹¹ Patient-reported Quality of Life (EQ-5D, EORTC-QLQ C30, EORTC-HCC18 and FACT-Hep) will be administered at Day 1 of Cycle 1 and Cycle 3, then at Day 1 every 3 cycle and at end of treatment s.

¹²Other stool tests and assays will include gut microbiota composition and/or metabolomic analysis.

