8.6.1 General Descriptive Analysis

The results will be presented of standard methods¹⁸:

- Continuous variables: Mean, 95%CI of Mean (95% mean confidence interval), SD (standard deviation), minimum, P25 (percentile 25), Median, P75 (percentile 75), maximum and N.
- Categorical variables: total frequency and percentages and for each category.
- Ordinal variables with few categories (less than 10) will be described using two tables: one including continuous variables descriptive parameters (as long as the interpretation is reasonable) and the other including categorical variables descriptive parameters. For ordinal variables with >10 categories, the same approximation used for continuous variables will be applied.

Where applicable, these summaries will be provided by time-point (scheduled time-point) including the absolute differences from baseline. The data of unscheduled time-points will be only listed. Additionally, only for the size of tumor the relative difference from baseline will be also described.

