8.6.2 Specific Descriptive Analysis

For the binary variables related to the primary and secondary outcomes, the estimation of rates and 95% CI will be performed by means of Clopper-Pearson exact method.

The Kaplan-Meier method will be used to describe the time to event endpoints, the median and their 95% CI. Analysis will follow censoring rules as described in section 8.5.1.

The continuous efficacy variable recruited by time-point will be analysed as a descriptively by means of the MMRM approach, fitting time-point as a fixed effect, and the subject and error terms as random. The dependent variable will be the absolute values (or absolute change from baseline when applicable). The within-patient variance-covariance matrix will be assumed to be unstructured. If this analysis fails to converge, the following structures will be tested in the following order until convergence: AR(1) (Auto-Regressive first order), Toeplitz and CS (Compound Symmetry). Time-point effects have been estimated by means of Least Square Means (LSM) and their standard error (SE) and 95% CI. Time-course evolutions have been estimated by LSM and their SE and 95%CI. The same analysis with a previous rank transformation applies to ordinal variables.

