8.6.5.3.3 EQ-5D

The items of EuroQoL-5D questionnaire (mobility, self care, usual activities, pain discomfort and anxiety depression) will be analysed according to the EQ-5D-3L user guide¹⁹. All item responses will be transformed in responses of three levels and two levels, as follows:

- Three levels: no problems, some problems and extreme problems
- Two levels: no problems and problems.

Descriptive statistical analyses by time-point will be performed for three levels response and for two levels response (as a continuous and as a categorical variable). Also, analyses by means of MMRM model with a previous rank transformation will be applied using three and two levels.

VAS EQ-5D will be analysed by the same MMRM.

8.6.5.3.4

FACT-Hep

Questionnaire FACT-Hep (version 4)²⁰ on clinical status included 45 items, 27 of which will be used for the determination of the following scale scores:

- Subscales:
 - Physical Well-Being subscale, PWB
 - Social/Family Well-Being subscale, SWB
 - Emotional Well-Being subscale, EWB
 - Functional Well-Being subscale, FWB
 - Hepatobiliary Cancer subscale, HCS
- FACT-G Total Score, FACTG
- FACT-Hep Trial Outcome Index (TOI)
- FACT-Hep total score

The individual items will be described as a continuous and as a categorical variable (see section 8.6.1) by time-point.

The subscales and the different total scores will be also described as a continuous variable and the MMRM will be applied.

8.6.5.3.5

EORTC-QLQ-C30

Questionnaire EORTC-QLQ-C30 (version 3)²¹ included 30 items and all of them will be used for the determination of the following scale scores:

- Global health status/QoL, QL2
- Functional scales:
 - Physical functioning, PF2
 - Role functioning, RF2
 - Emotional Functioning, EF
 - Cognitive functioning, CF
 - Social functioning, SF
- Symptom scales
 - Fatigue, FA
 - Nausea and vomiting, NV
 - Pain, PA
 - Dyspnoea, DY
 - Insomnia, SL
 - Appetite loss, AP
 - Constipation, CO
 - Diarrhoea, DI
 - Financial difficulties, FI

The individual items will be described as a continuous and as a categorical variable (see section 8.6.1) by time-point.

The scales scores will be also described as a continuous variable and the MMRM will be applied.

8.6.5.3.6

EORTC QLQ-HCC18

Questionnaire EORTC-QLQ-HCC18²² is a supplementary questionnaire module to be employed in conjunction of QLQ-C30 (is a Hepatocellular Carcinoma Module), included 18 items and all of them will be used for the determination of the following scale scores:

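### The SAP 8.6.2 repeated-measures model sets no limit on visits, and its fallback structures assume one variance at every visit, so intervals for change from baseline can be too wide early and too narrow late

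*SAP*

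**What the plan says.** SAP 8.6.2 defines one mixed model for repeated continuous variables, "fitting time-point as a fixed effect, and the subject and error terms as random". On the outcome it says "The dependent variable will be the absolute values (or absolute change from baseline when applicable"). On covariance it says "The within-patient variance-covariance matrix will be assumed to be unstructured", and after non-convergence "structures will be tested in the following order until convergence: AR(1) (Auto-Regressive first order), Toeplitz and CS (Compound Symmetry"). Least-squares means, standard errors and 95% intervals are to be reported.

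The model is applied to laboratory and vital-sign variables (SAP 8.6.5.3), tumour size (8.6.5.3.1) and the quality-of-life scales (8.6.5.3.3 to 8.6.5.3.6). SAP 8.6.1 keeps unscheduled visits out of the summaries ("The data of unscheduled time-points will be only listed"), but nothing limits how many scheduled visits enter the model. The planned size is "7 sites / 40 patients" (Protocol synopsis).

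Quality of life "will be administered at Day 1 of Cycle 1 and Cycle 3, then at Day 1 every 3 cycle and at end of treatment" (Protocol Table 5, footnote 11, repeated in SAP 7.7). The Protocol synopsis puts laboratory visits every 2 weeks for two months and then every 4 weeks, and imaging at week 4 and then every 8 weeks.

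**The concern.** There are three difficulties.

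- An unstructured matrix over t visits has t(t+1)/2 parameters, and later visits must still contain enough patients to estimate them. A random subject effect added to an unstructured or CS matrix is not identifiable.
- The fallback is triggered by convergence, not by fit. AR(1) is a special case of Toeplitz and has only two parameters, so it converges readily and the search stops there.
- AR(1), Toeplitz and CS, as listed, each have one variance for all visits. Change from baseline often does not: its variance rises with time when correlation decays or when scores spread out.

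At stake are the error bars that the SAP commits to report. SAP 8.5 also relies on this model, and explicitly on its covariance structure, to deal with missing continuous data.

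**Working it through.** The documents give no visit count, SD, correlation or dropout figure for this model, so there is no stated figure to reproduce.

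**Inputs.** N = 40 and a planned treatment duration of 24 months (Protocol synopsis); visit schedules as above. Time on treatment is an assumption: exponential with median 5.2 months (22.6 weeks), borrowed from the median PFS in Protocol 1.2.3; medians of 4 to 18 months were also tried.

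**Step 1: number of parameters.** 24 months is 26 cycles of 28 days.

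| Schedule | Time-points t | t(t+1)/2 |
|---|---|---|
| Laboratory | 26 day-1 + 2 day-15 = 28 (29 with end of treatment) | 406 (435) |
| Imaging | baseline + weeks 4, 12, ..., 100 = 14 | 105 |
| Quality of life | weeks 0, 8, 20, ..., 92 = 9 (10 with end of treatment) | 45 (55) |

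**Step 2: estimability.** Under monotone dropout an unstructured matrix needs at least t + 1 patients at visit t. Expected patients at week w: n(w) = 40 × 0.5^(w/22.6).

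- Quality of life: visit 6 (week 56) has 7.2, needs 7, passes; visit 7 (week 68) has 5.0, needs 8, fails.
- Imaging: visit 7 (week 44) has 10.4, needs 8, passes; visit 8 (week 52) has 8.1, needs 9, fails.
- Laboratory: visit 12 (week 36) has 13.3, needs 13, passes; visit 13 (week 40) has 11.7, needs 14, fails.

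A 12-month median makes all 9 quality-of-life visits estimable, and an 18-month median all 14 imaging visits. The 28 laboratory visits are never estimable (at most 20). Simulated unstructured fits converged in 100% of runs with four quality-of-life visits and 97% with five (100 runs each).

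**Step 3: fallback.** In simulation (N = 40, REML), AR(1) converged in 100% of runs in every scenario, and in 97.5-100% with a random subject effect added.

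**Step 4: the one-variance assumption, by hand.** Suppose variance is constant and correlation decays as 0.7 per 8 weeks (assumed). In units of the single-visit variance, change from baseline has variance v(w) = 2(1 − 0.7^(w/8)). A one-variance model uses roughly the average of v weighted by n, and coverage is about 2Φ(1.96 × √(pooled/v)) − 1.

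*Quality of life*, weeks 8, 20, 32, 44: n = 31.3, 21.7, 15.0, 10.4; v = 0.600, 1.180, 1.520, 1.719. Pooled = (18.8 + 25.6 + 22.8 + 17.9)/78.4 = 1.085.
- Week 8: √(1.085/0.600) = 1.345, coverage 99.2%.
- Week 44: √(1.085/1.719) = 0.794, coverage 88.1%.

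*Laboratory*, weeks 2, 4, 6, 8, then every 4 weeks to 36: n = 37.6, 35.4, 33.3, 31.3, 27.7, 24.5, 21.7, 19.2, 17.0, 15.0, 13.3; v = 0.171, 0.327, 0.469, 0.600, 0.829, 1.020, 1.180, 1.314, 1.426, 1.520, 1.598. Pooled = 219/276 = 0.795.
- Week 2: ratio 2.16, coverage about 100%.
- Week 36: ratio 0.705, coverage about 83%.

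A random subject effect adds the same amount to the variance at every visit, so it does not change this.

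**Step 5: simulation.** Coverage of nominal 95% intervals, AR(1), change from baseline as outcome, 5.2-month median:

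| Assumed truth | Quality of life, week 8 → 44 | Imaging, week 4 → 44 |
|---|---|---|
| Decay 0.7 per 8 weeks | 98.9% → 89.0% | 100% → 88.2% |
| Subject effect plus decay | 97.0% → 92.5% | 97.8% → 92.5% |
| Same, SD growing 1.5-fold | 97.7% → 88.9% | 98.5% → 88.2% |
| Constant correlation 0.6 | 95.6% → 95.7% | 94.2% → 96.0% |

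(1,500 runs for quality of life, 400 for imaging.) For laboratory change under decay or growing variance, coverage ran from about 100% early to 77-88% late. The last row follows from Step 4: with constant correlation, v = 2(1 − 0.6) = 0.8 at every visit, so one variance is correct.

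**The case against.** The strongest objection concerns how AR(1) goes wrong. A reader might infer that AR(1) forces correlation towards zero at long lags and so inflates standard errors 1.3- to 1.7-fold. For example, with true constant correlation 0.5 and six visits, the SE is about √(2(1 − 0.04)/40) = 0.219 against a true √(2(1 − 0.5)/40) = 0.158. The SAP does not support this reading. The inflation arises for a last-minus-first contrast of absolute values under AR(1) without the random subject effect that 8.6.2 includes. With that effect, the model contains constant correlation as a special case; the ratio of SE to true SD was then 0.93-1.05 and coverage 94.5-95.5% in one simulation, and coverage about 91-97% for quality of life in another. This part of the objection stands.

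Other limits also stand:

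- It would be too strong to say that the model cannot be fitted with 40 patients: that depends on how many visits enter, and four or five quality-of-life visits fit.
- Unequal spacing is not the main cause. Imaging is regular after the first gap, and a structure using actual weeks was no better under constant correlation.
- Reordering the structures would not be enough: with growing SD, Toeplitz covered 85-98% and CS 83-98% for quality of life.
- For EQ-5D, "analyses by means of MMRM model with a previous rank transformation will be applied using three and two levels" yields means of ranks that are hard to read, but the two-level (no problems or problems) description by visit is already planned (SAP 8.6.5.3.3, Table 30).
- SAP 8.6 calls the analyses non-inferential, and 8.6.1 also gives raw means with 95% intervals.

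The last point limits the consequence but does not remove it. Raw means use available data only, whereas SAP 8.5 justifies the mixed model by its behaviour when data are missing at random.

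**Conclusion.** The point holds as a specification gap in descriptive analyses. The unstructured matrix is not estimable for the full laboratory schedule at any attrition tried, nor for the full quality-of-life and imaging schedules at a median near 5 months on treatment. The plan then settles on AR(1) in practice. When change from baseline is analysed and correlation decays or variance grows, its model-based intervals are too wide early (about 98-100% coverage) and too narrow late (about 77-90% in most scenarios, 92.5% in the mildest), with or without the subject effect. Under constant correlation the planned model is about nominal, so a general claim of wrong or uniformly inflated intervals is not supported.

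The coverage figures rest on assumed covariance structures and exponential dropout; the documents supply neither. Quality-of-life, laboratory, vital-sign and tumour-size tables are affected. The primary safety rates, ORR, OS, TTP and PPS do not use this model.

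**What to change.** Amend SAP 8.6.2 as follows.

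- Include only scheduled visits with at least 10 patients, and summarise end of treatment separately, since it has no fixed study time.
- Omit the random subject effect when the matrix is unstructured or CS.
- Whenever a fallback structure is used, report empirical (sandwich) standard errors with a small-sample correction, and degrees of freedom based on the patients at that visit.

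The cap alone is not enough. With a 5.2-month median, n(w) ≥ 10 holds to about week 45 (2 × 22.6). That leaves 5 quality-of-life, 7 imaging and 14 laboratory time-points. At week 44, 10.4 patients are expected, against 6, 8 and 15 needed, so laboratory data would still use a fallback and need the sandwich errors. In simulation with at least 10 patients per visit, these restored coverage to roughly 90-97%.

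The cost is SAP wording and minor programming. The downside is that late visits are summarised or listed, not modelled. Selecting the structure by an information criterion, or adding baseline as a covariate, would be a preference and is not needed.

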8.6.3 Definitions and derivation of data

The following definitions and derivations will be used for this study:

- The analyses will be performed by visits and the baseline values for the calculation of the differences (absolute or relative) with respect to the baseline using the following strategy:
 - Baseline values will be defined as the last measurement taken before the first administration.

- The value of the baseline visit in case of measurement existing in that visit.
- The value of the screening visit if there is no measurement in the baseline visit.
- Start of the treatment period will be defined as the date of inclusion
- Absolute differences from baseline for each visit:
 - Absolute differences = observed value - baseline value
- Relative differences from baseline (only for the size or tumour):
 - Relative difference = [observed value-baseline value] / baseline value

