Follow-up will include clinical and laboratory assessment every 2 weeks within the first 2 month, then every 4 weeks, tumor evaluation at week 4 and every 8 weeks thereafter. In addition, unscheduled visits will be made should they be needed (adverse events or symptoms). At each time point that the dose is changed we will perform a blood extraction to determine serum biomarkers. Moreover, a second extraction will be done 7 days after modifying the cabozantinib dose. Adverse events will be graded following version 5.0 of the CTCAE of the National Cancer Institute, during treatment and 30 days after the last dose. Tumor evaluation during follow-up will be evaluated by CT-scan. Response and TP will be defined according to the RECIST criteria v1.1. Outcomes will be measured from the date of starting cabozantinib until the date of death regardless of cause of death. TTP will be defined as the time from the starting date of cabozantinib to disease progression (according to RECISTv1.1). PPS will be measured from the date of detecting progression at radiology until the date of death or

last follow-up. Assessment will be done by radiologists in each center and then a central revision by radiologists with more than 10 years of experience in HCC and blinded to the evolution and outcome of the patients. Disease-control rate (DCR) will be defined as the percentage of patients who had a best-response rating of complete response (CR), partial response (PR) or stable disease (SD) (according to RECIST and BCLC-RECIST) maintained for at least 28 days after the first demonstration of best-response rating as per independent radiologic review.

Statistical & Analytical Plan and Methodology

The study will be analyzed using standard statistical methods to estimate rates and 95%CI (for ORR and other binary variables) by means of the Clopper-Pearson exact method, and the Kaplan-Meier method to describe the survival functions and the median and [95%CI]. A Statistical Analysis Plan, which will include all details regarding all analyses, the interim method, the handling of missing data and any plan for the analysis, will be finalized before the initiation of the study recruitment.

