8 STATISTICAL ANALYSIS

8.1 ANALYSIS POPULATIONS

There are only one population for this study:

- Safety Set: All eligible patients who have received at least one dose of Cabozantinib will be included in the Safety population.

The population will be fully defined and documented during the Data Review and before the database lock. The objective will be to carry out the population selection and definition of the final study population.

The Safety population will be used for all analysis including the efficacy secondary endpoints.

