8.3.2 Secondary outcomes

ORR will be the first relevant ranked secondary outcome:

- Defined as a partial or complete response at any time, i.e. the best response from inclusion along all follow-up.

The rest of secondary end points are:

1. Time to progression (TTP): time to the first progression, defined as the time from the inclusion date to progression (i.e. date of progression event or censoring – date of inclusion + 1).
2. Pattern of progression:
 - Intrahepatic growth (IHG): increased size of intrahepatic target lesions or progression of intrahepatic "non-target" lesions at baseline.
 - New intrahepatic lesion (NIH): emergence of new intrahepatic lesions
 - Extrahepatic growth (EHG): increased size of extrahepatic target lesions, progression of extrahepatic "non-target" lesions at baseline or progression of the existing vascular invasion.
3. Rate of patients who develop new extra-hepatic spread

4. Overall survival (OS): defined as the time from the inclusion date to death from any cause (i.e. date of death event or censoring – date of inclusion + 1).
5. Post-progression survival (PPS), for those patients who progressed, the time from the progression date to death from any cause (i.e. date of death event or censoring – date of 1st progression + 1).

Please see description of the censoring rules for time to event variables in section 8.5.1.

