8.5.1 Censoring rules

TPP:

- Death without progression will be censored at the time of the last adequate radiological tumor assessment.
- Progression documented between scheduled assessments: Event at date of adequate radiological tumor assessment
- If a patient has not progressed at the time of database cutoff, the TPP of this patient will be censored at the last adequate tumor assessment before the database cutoff.
- Documented progression or death after missing ≥ 2 consecutive post-baseline tumor assessments: date of last adequate tumor assessment before missed assessments or date of inclusion, whichever is later.
- Patient lost to follow-up (or withdrew consent from study participation) before documented progression: date of last adequate tumor assessment.
- Please see comment below on the “treatment policy” and “while on treatment” estimands

Overall survival (OS):

- If a patient is alive at the time of last contact before the database cutoff, the OS of this patient will be censored at the date of last contact.
- Patient lost to follow-up (or withdrew consent from study participation) before death: date of last documented alive information
- Please see comment below on the “treatment policy” and “while on treatment” estimands

Post-progression survival (PPS)

- Same rules as OS

Handling of “treatment policy” and “while on treatment” estimands: If a patient discontinues study treatment or any other ICE is recorded before any event is documented, data from this patient will not be censored for the primary estimand (treatment policy). However, data will be censored for the supplementary estimand (while on treatment) at the last tumor assessment before the discontinuation of study treatment.

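### The SAP times OS, TTP and the treatment period from an undefined inclusion date; the protocol times outcomes from the start of cabozantinib

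*SAP*

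**What the plan says.** The protocol synopsis (Follow-up period) gives one time origin: "Outcomes will be measured from the date of starting cabozantinib until the date of death regardless of cause of death". For TTP it is explicit: "TTP will be defined as the time from the starting date of cabozantinib to disease progression". Protocol section 9 does not restate an origin.

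The SAP uses a different one. In 8.3.2, TTP is "defined as the time from the inclusion date to progression" and OS is "defined as the time from the inclusion date to death from any cause". In 8.5.1, a TTP event that follows two or more missed tumour assessments is censored at the "date of last adequate tumor assessment before missed assessments or date of inclusion, whichever is later". In 8.6.3, "Start of the treatment period will be defined as the date of inclusion", although the same section ties baseline to a different date: "Baseline values will be defined as the last measurement taken before the first administration".

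There is one analysis set (SAP 8.1): "All eligible patients who have received at least one dose of Cabozantinib will be included in the Safety population". SAP 8.5 adds that patients who never start treatment are excluded.

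Neither document says what inclusion is. Protocol 4.1.1 defines study entry as the date of consent, allows at most 28 days from then to first dose, and assigns an enrolment number at an unspecified point after eligibility has been documented.

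**The concern.** The SAP departs from the protocol's time origin without giving a reason, and the date it substitutes has at least three candidate meanings: consent, enrolment or first dose. Two programmers could derive different medians from the same data.

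The direction of the error is fixed. A patient who dies between inclusion and first dose is never analysed, so that interval is immortal time for OS. For TTP the interval is also guaranteed free of deaths. It is free of progression in practice, because the schedule has no tumour assessment between screening and first dose. If inclusion precedes dosing, both medians can only get longer. This matters beyond tidiness because protocol 9.1 plans indirect comparisons of the study's confidence intervals with external data.

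There is a second possible route, into the primary endpoint. AEs are recorded from consent (protocol 7.2.1), the primary outcome covers the time on treatment plus 30 days (SAP 8.3.1), and the treatment-emergent tables have no onset rule (SAP 8.6.5.3.7). If the treatment period begins at inclusion, a grade 3 or higher event before the first dose could be counted. The mandatory pre-treatment biopsy is one plausible source. That would count against the drug an event it cannot have caused. No sentence in either document states this; it follows only from reading the sections together.

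**Working it through.** The plan gives no figure of its own to reproduce; the 28 days is a limit set in protocol 4.1.1.

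**Inputs**
- Maximum time from consent to first dose: 28 days (protocol 4.1.1).
- Eligibility laboratory tests due within 7 days before therapy (protocol 5.1.2).
- Reference medians, for scale only: OS 10.2 months and PFS 5.2 months with cabozantinib in the cited phase 3 trial (protocol 1.2.3). The documents give no TTP median. PFS is a stand-in: it counts death as an event, whereas TTP censors it.
- Month length: 30.4375 days.
- Planned sample: 40 patients.

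**Step 1: added time under each meaning of inclusion.** Added time = first-dose date − inclusion date.
- First dose: 0 days.
- Enrolment number: between 0 and 28 days. It is about 7 days or less if the number is issued after the qualifying laboratory results and those are not repeated later.
- Consent: up to 28 days.

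**Step 2: a fixed lag, the same for every patient.** Shift in months = days / 30.4375; relative shift = shift / reference median.

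| Lag | Shift (months) | Against 10.2 (OS) | Against 5.2 (PFS as stand-in) |
|---|---|---|---|
| 7 days | 0.23 | 2.3% | 4.4% |
| 14 days | 0.46 | 4.5% | 8.8% |
| 28 days | 0.92 | 9.0% | 17.7% |

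At 28 days a true 10.2-month median would be reported as 10.2 + 0.92 = 11.12 months, and a true 5.2-month median as 6.12 months.

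**Step 3: a lag that varies between patients.** Assume exponential times from first dose plus a lag spread evenly over the range. Simulation moves the median by about 0.12 months for 0–7 days and about 0.46 months for 0–28 days. This is close to the mean lag: 3.5 / 30.4375 = 0.115 and 14 / 30.4375 = 0.46.

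**Step 4: adverse events.** Each patient whose only critical AE occurs before dosing would add 1/40 = 2.5 percentage points to the primary rate, if such events are counted.

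**Step 5: the censoring fallback.** The SAP computes time as censoring date − origin + 1. As written, origin and fallback are both inclusion, giving 0 + 1 = 1 day. If the origin alone moved to first dose and inclusion was 28 days earlier, the result would be −28 + 1 = −27 days. The two dates must therefore change together.

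**The case against.** The strongest reply is that SAP 8.6.3 is itself the reconciliation: by starting the treatment period at inclusion, it makes inclusion day 1 of treatment, and the shift is zero. Some usage supports this. The visit schedule runs from screening to day 1 with no enrolment visit between. The protocol's word for the consent date is study entry, and patients who withdraw before treatment are screening failures. SAP 8.3.2 counts best response from inclusion where protocol Appendix 3 counts it from the start of treatment, as if the terms were synonyms. The reading is possible, but the sentence defines the treatment period by inclusion, not inclusion by dosing. The same section uses first administration as a separate anchor, and SAP 8.5 has a rule for patients who never start. The zero case belongs in the range; it does not remove the need for a definition.

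It is also fair that 28 days needs both the consent reading and the longest wait for everyone, and that the 7-day limit dates laboratory tests, not enrolment. Both figures are conditional.

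On materiality, SAP 8.6 declares the analyses non-inferential. With 40 exponential times, a 10.2-month median and no censoring, the sample median has a 95% sampling range of about 6.4 to 15.4 months. Shifts of 0.12 and 0.46 months are about 1% and 5% of that width. For TTP, a lag of 7 days or less is within the scan window of ±7 days. This limits the harm, but a one-directional error is not removed by noise around it.

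Finally, terms such as during treatment and treatment-emergent ordinarily exclude pre-dose events. That is why the AE point stands only as an inference.

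**Conclusion.** The concern holds. The SAP's stated origin for OS and TTP contradicts the protocol's and rests on a term that neither document defines. On any reading of inclusion that falls before first dose, the SAP followed as written reports longer OS and TTP than the protocol's definition would.

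The size is 0 to 28 days, assuming the screening window is respected. The top of the range is an extreme, not an expected value. Post-progression survival starts at progression and is unaffected. The harm is to the accuracy of descriptive medians and their comparison with external data, not to a test. The effect on the primary AE rate would run the other way, raising it, and depends on pre-dose events being admitted. This should be corrected, but it does not threaten the trial's main conclusion. Confidence is moderate, because the true shift depends on a definition the documents do not supply.

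**What to change.** In SAP 8.3.2, 8.5.1 and 8.6.3, replace inclusion with the date of first dose of cabozantinib, as in the protocol: as the origin for OS and TTP, as the fallback censoring date for TTP, and as the start of the treatment period. Change the origin and the fallback date together.

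In SAP 8.3.1 and 8.6.5.3.7, count in the primary and treatment-emergent analyses only AEs with onset on or after first dose and up to 30 days after last dose. List pre-dose AEs separately.

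The cost is SAP wording. The first-dose date is already needed to define baseline, so no new data are required. The reported medians may be slightly shorter.
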